### Confidentiality and Source Data

Only key study personnel at the Data Coordinating Center, Vanderbilt University, will have access to the full study dataset which will be maintained in REDCap.

### Data Safety and Monitoring

The interim analysis will be conducted by VICTR biostatistician [name] and Data Safety Monitor, [name], Assistant Vice Chancellor for Translational Science. The results will be reviewed with the 3 member Safety Monitoring Committee including [name], VUMC Adult Enterprise Quality Committee: [name], CEO of Vanderbilt University Adult Hospital and Clinics; and [name], Chief Quality, Patient Safety and Risk Prevention Officer for VUMC. In addition to the study data analysis the Safety Committee will review 1) a 10% sample of the Phone Call Nurse's daily reports to her supervisors which is an element of clinical care reporting and 2) a summary of potential safety concerns from the office overseeing this clinical program, the Medicine Patient Care Center. The study team will remain blinded to outcome associated results.

#### Sample Size Considerations

Per inpatient hospital admission volume from October 2015 - September 2016, we estimate approximately 3048 patients will eligible for the study over the 6 month study period. Of those ½ will be randomized to each study arm. Based on the experience of a current pilot with calls made by 1 nurse, we anticipate attempting to call 1117 patients and reaching 334 patients in the phone call group each month. We will analyze the impact of the program on the phone call population with a pre-specified subgroup analysis of those actually reached (See Figure 1 – Study Design Schematic and Enrollment Projection).

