#### **Study Summary**

Study Start: February 13, 2017 (1 week run-in period) Accrual Start: February 20, 2017 (NCT03050918) Primary Outcome: Readmission within 30 days

[figure not shown]
Primary Analysis: Intention to Treat

- Study length/accrual period: ~7 months
- Follow up: 45 days
- Sample size: 3556 (1778 per arm)
- Baseline event rate = 13.5%
- Target detectable difference of 3.5% (13.5% controls, 10% intervention)
- Power 90% (chi square)

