### **ANALYSIS PLAN**

#### General Approach

The study analysis will have 3 phases. The primary analysis will examine our primary outcome, hospital readmission within 30 days, via an intention-to-treat analysis where comparisons will be made between the 2 study arms. We will then examine secondary outcomes of all cause ED visits to Vanderbilt or VHAN ED and mortality. Given VUMC's interest in understanding characteristics of patients not reached via telephone, we will explore differences among those called and reached, called and not reached, and the control arm. In these 3 phases we will examine outcome differences by treatment assignment, age, gender, race, highest educational attainment, health literacy, established primary care status, patient satisfaction level, Medicare readmission penalty diagnosis status, and readmission risk score calculated at discharge as part of routine care at VUMC. Lastly, we will use descriptive statistics to quantify the need for patient assistance with discharge plan implementation (appointment scheduling or reminders, questions about new medications, durable medical equipment acquisition, referral for new symptoms, etc.) among patients in the intervention arm who are called and reached.

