**Table 1 - Power and Sample Size Scenarios** 

	Conse	rvative	Ambitious	
Control Group Readmission Rate†	13.52%	13.52%	13.52%	13.52%
Intervention Group Readmission Rate	9.60%	9.10%	10.20%	9.70%
Power	80%	90%	80%	90%
Detectable Difference	3.9%	4.4%	3.3%	3.8%
Projected Study Sample Size	1117	1117	1582	1582

\*2 group X^2 test of equal proportions (equal n's), 2-sided text, final analysis  $\alpha$  = 0.048

illustrate conservative and ambitious enrollment scenarios with estimates for 80% and 90% power. Considering we have 1 Phone Call Study Nurse and will miss enrollment days for paid time off or sick days, we opted for a more conservative power target and detectable differences of 80% and 3.9% respectively. This carries an associated enrollment of 1117 patent per arm (n = 2234, or 11 patients per day).

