### **Appendix IV- Study Variable Summary**

#### Phone Call Study Patient Variates

BASELINE PATIENT DATA
First name
Last name
Zipcode
Medical record number
Established Primary Care Yes
No

Health Literacy BHLS Education level

Race Black White

Latino Non-white Hispanic

Multiple Races Unknown

Primary Language English

Spanish Arabic Other

Number of Hospitalizations in Prior Year

Complicating Baseline Comorbidities (Natural Language Processing)

Congestive heart failure

COPD

Readmission penalty dx - AMI, HF, PNA, COPD,

CABG, Total hip/knee repair, and stroke

Diabetes

Outpatient hospice Substance abuse Depression INDEX HOSPITALIZATION DATA

Intervention Arm Encounter Number Date of admission Time of admission

Admission day of the week Admission Diagnosis #1 Admission Diagnosis #2 Admission Diagnosis #X Highest bed level

Floor ICU Discharge Service Riven Morgan

> Geriatrics Palliative Care

Discharge Diagnosis #1 (ICD-10)
Discharge Diagnosis #2 (ICD-10)
Discharge Diagnosis #3 (ICD-10)
Discharge Diagnosis #4 (ICD-10)
Discharge Diagnosis #X (ICD-10)

Discharge Date Discharge Time

Discharge Location/Disposition

Readmission penalty dx cohort- AMI, HF, PNA, COPD, CABG, Total hip/knee repair, and stroke

Number of medications upon discharge

VUMC Cornelius Readmission Risk Score Patient satisfaction (Press Ganey Score, 1-5)

READMISSION HOSPITALIZATION DATA

Date of admission Time of admission Admission Diagnosis #1 Admission Diagnosis #2

Admission Diagnosis #X Highest bed level Floor

ICU
Discharge Diagnosis #1 (ICD-10)
Discharge Diagnosis #2 (ICD-10)
Discharge Diagnosis #3 (ICD-10)

Discharge Diagnosis #4 (ICD-10)

Discharge Diagnosis #X (ICD-10)

Readmission penalty dx - AMI, HF, PNA, COPD, CABG, Total hip/knee repair, and stroke

Discharge Date
Discharge Time
Discharge Location

Patient satisfaction (Press Ganey Score, 1-5)

Extra-Institutional Data

Survival Data (at 30 days)

Non-VUMC TN Readmission (at 30 days post VUMC

admit)

(minimum data = yes/no)

CALL INTERVENTION DATA

1st Contact

Time of first call Date of first call

Final Contact

Time of Final Contact Date of Final Contact

Call attempts

1 2 3

Not eligible AMA Facility Placement Deceased

Already seen in clinic CRC patient

Patient currently admitted/readmitted

Call status

Success

Unsuccessful - Wrong Number

Unsuccessful - Refused

Unsuccessful - Patient Call Back Requested

Unsuccessful - Patient Not Available

Unsuccessful - No Answer

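### Secondary and exploratory analyses only: the reached-patient impact analysis and the satisfaction subgroup use groups formed after randomisation, and neither can be read as a call effect (minor)

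*Combined protocol and SAP*

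**What the plan says.** The primary analysis is by intention to treat between the two randomised arms (Study Summary; General Approach). Significance and Impact ties the decision on whether to invest in the programme to the primary endpoint, and uses the secondary results to shape the programme's design.

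*Reached patients.* Sample Size Considerations promises: "We will analyze the impact of the program on the phone call population with a pre-specified subgroup analysis of those actually reached". That sentence refers to Figure 1, which is not shown in the copy reviewed. General Approach adds that "we will explore differences among those called and reached, called and not reached, and the control arm", and then says outcome differences will be examined in all three phases of the analysis. The list of secondary analyses in the Study Summary, by contrast, gives only descriptive demographics for these three groups.

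*Timing.* Randomisation is the morning after discharge (Study Length and Timeline). Up to three call attempts may be made until day 7 (Study Arms).

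*Call coding.* In Appendix IV the reasons for not being eligible for a call appear to include "Patient currently admitted/readmitted" and "Already seen in clinic". Call status has an unsuccessful category for a patient in hospital and an unnecessary category for one already seen in clinic.

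*Satisfaction.* Outcome Measures and General Approach list it among the factors by which readmission is examined: "established primary care status, patient satisfaction level, Medicare readmission penalty diagnosis status". Outcome Measures and the Outcome Analysis list in Appendix V also treat it as an outcome. Appendix IV places the Press Ganey score under index-hospitalisation data. The closing part of the call script (Appendix I) tells the patient that a survey about the hospital stay will arrive by post and asks for it to be completed.

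**The concern.** A subgroup effect is protected by randomisation only if the subgroup could be identified in both arms before treatment had a chance to act. Neither grouping meets that condition.

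Reached patients exist only in the call arm. Who is reached depends on who answers, who has already been seen in clinic, and who is already back in hospital. The last of these is the primary outcome itself. Controls keep all their early readmissions, while the reached group tends to lose some of its own.

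Satisfaction ratings and survey response may both depend on the call and on readmission. A difference in call effect between satisfaction levels could then arise from how the levels were formed.

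What is at stake is the programme's design. A reached-patient result labelled as impact, or a satisfaction interaction taken as a call effect, could mislead there.

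**Working it through.** **1. Order of events.** Randomisation is the morning after discharge, calls run to day 7, and readmission is counted to day 30. Reach is therefore fixed after randomisation, inside the outcome window and in one arm only. This follows from the text whatever Figure 1 shows.

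**2. Reach rate.** The plan states: "we anticipate attempting to call 1117 patients and reaching 334 patients in the phone call group each month". 334/1117 = 29.9%, which matches the 30% reach given under Potential Risks and Benefits. The monthly label does not fit the Power Calculation, where 1117 is the total per arm ("This carries an associated enrollment of 1117 patent per arm"). The Study Summary gives another size ("Sample size: 3556 (1778 per arm"). The early-readmission illustration in step 3 does not depend on sample size.

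**3. Early readmission alone, with no call effect.**

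- From the plan: 30-day risk p = 0.1352 (Power Calculation); calls possible up to day 7.
- Assumed, because the documents give no contact or readmission timing: contact at day t, from 1 to 7; time to readmission either with constant hazard (shape k = 1) or front-loaded (Weibull shape k = 0.75); and q, the chance of being reached if readmitted before contact, relative to other patients.

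Formulas:

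- L = −ln(1 − 0.1352) = 0.1453
- Readmitted before contact: e = 1 − exp(−L·(t/30)^k)
- Risk among the reached: (q·e + p − e)/(q·e + 1 − e)
- Spurious benefit: p minus that risk

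| k | t (days) | e | Spurious benefit, q = 0 | Spurious benefit, q = 0.5 |
|---|---|---|---|---|
| 1 | 1 | 0.0048 | 0.42 points | 0.21 points |
| 1 | 3 | 0.0144 | 1.27 | 0.63 |
| 1 | 7 | 0.0333 | 2.98 | 1.47 |
| 0.75 | 1 | 0.0113 | 0.99 | 0.49 |
| 0.75 | 3 | 0.0255 | 2.26 | 1.12 |
| 0.75 | 7 | 0.0476 | 4.32 | 2.11 |

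Example (k = 0.75, t = 7, q = 0): (0.1352 − 0.0476)/(1 − 0.0476) = 0.0920, and 13.52% − 9.20% = 4.32 points. The upper end requires everyone to be contacted on day 7 and no early-readmitted patient to be reached later, so it is an extreme.

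**4. A component whose direction is open.** Suppose a fraction f of the call arm is diverted as already seen in clinic and has r times the risk of the rest (both assumed). Risk in the rest is p/(f·r + 1 − f).

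- r = 0.5: 14.23% at f = 0.1 and 15.02% at f = 0.2, a shift of 0.7 to 1.5 points against the call.
- r = 1.5: 12.88% and 12.29%, a shift of 0.6 to 1.2 points in favour of the call.

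Who answers the phone is a further selection, and it can also work in either direction.

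**5. Satisfaction.** No arithmetic applies. The script describes a survey still to come at the time of the call. Only patients who are reached hear the request to complete it, so response may differ by arm. That this survey supplies the satisfaction score is an inference. The visible text does not say how survey non-response is handled.

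**6. Precision of a complier-average estimate.** The half-width of the 95% interval for the intention-to-treat risk difference is 1.96·√[(p0(1 − p0) + p1(1 − p1))/n].

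| n per arm | p1 | Half-width, ITT | Divided by 0.299 |
|---|---|---|---|
| 1117 | 13.52% | 2.84 points | 9.5 points |
| 1117 | 9.6% | 2.65 | 8.9 |
| 1778 | 13.52% | 2.25 | 7.5 |
| 1778 | 9.6% | 2.10 | 7.0 |

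**The case against.** **The reached analysis may be descriptive only.** The Study Summary lists descriptive demographics, General Approach gives its motive as understanding the patients not reached, and the Objective calls subgroup information exploratory. This limits the point but does not remove it. General Approach also promises outcome differences in all three phases, and Sample Size Considerations uses the word impact.

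**Figure 1 may supply detail.** A reader might infer that the plan has no comparator or method for the reached analysis. The documents do not support that: the visible text gives none, but the sentence points to a figure that is not shown. Absence from Appendix V is weak evidence too, because that appendix is the interim plan and the Study Timeline defers a reachability index beyond the interim analysis. No comparator in Figure 1, however, could make reach a randomised grouping.

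**The coding evidence is imperfect.** The lists in Appendix IV are flattened, so their hierarchy is partly inferred. With three attempts to day 7, a patient in hospital at one attempt may still be reached later. Complete exclusion of early readmissions (q = 0) is therefore an extreme, which is why q = 0.5 is also shown.

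**Satisfaction concerns the index stay.** Appendix IV files it there and the survey asks about the stay, which precedes randomisation. That is fair as to its subject. It does not make the rating or the response a baseline measurement if the survey is completed after the call or after a readmission.

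**Conclusion.** The point holds for secondary and exploratory analyses, at minor severity. Reached against control is not a randomised comparison, and satisfaction is not a baseline factor. The first conclusion rests on the stated timing alone. The second rests on the script's survey being the source of the score.

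Three stronger readings are tempting and not supported:

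- *The reached analysis favours the call.* Only the early-readmission component has a known direction. Clinic diversion and who answers could add to it or offset it, so the net direction and size are unknown. The ranges of 0.4 to 4.3 points (q = 0) and 0.2 to 2.1 points (q = 0.5) illustrate that one component under assumed timing; they do not estimate the bias.
- *A particular false-positive rate follows.* The visible text states no test or alpha for the reached analysis.
- *The trial's main conclusion is at risk.* The primary intention-to-treat comparison is untouched, and the investment decision rests on it.

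The bias in the satisfaction subgroup cannot be sized from the documents.

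**What to change.** - **Sample Size Considerations:** replace the reached-subgroup impact analysis with a descriptive account of reached patients.
- **General Approach:** keep the reached, not reached and control groups as descriptive, label them non-randomised, and state that no outcome difference among them will be read as a call effect.
- **Outcome Measures and General Approach:** remove patient satisfaction from the subgroup factors for readmission, keep it as an outcome, and report survey response by arm.
- **Optional, only if an effect in those reached is wanted:** pre-specify a complier-average estimate with its confidence interval. This is the intention-to-treat risk difference divided by the proportion reached among all patients analysed in the call arm. State that it assumes no effect without contact, which is open to question because a message left counts as an unsuccessful call, and that it is imprecise: a 95% half-width of about 7 to 9.5 points at 30% reach.

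The cost is a change of SAP wording with no new data. A direct effect estimate in reached patients and one subgroup analysis are given up. The optional estimate would need a few lines of code.

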### Study Length and Timeline

The informatics run-in period will begin February 7th, 2017 to test the Study Data Flow and integrity of the randomization process. Official study enrollment will begin February 20th, 2017. Patients will be randomized the morning after hospital discharge. Those receiving a call will be contacted within 7 days of hospital discharge. We will obtain interim impact estimates of the discharge phone call intervention at 50% enrollment for 80% power (See the *Study Timeline*, on page 2), and conduct the definitive analysis at 100% enrollment. In addition, the analyses will account for a 30 day re-admission observation window. Fifteen additional days will be added to the follow-up period to assure re-admissions are not minimally deferred to just after the 30 days period. Run-in period patient cases will be used to test the study data extraction and database upload process prior to the planned study analyses. This will permit us to troubleshoot unforeseen data collection challenges. Given the sample size considerations noted above, we estimate a study length of 7 months with enrollment completion in September of 2017, primary outcome follow-up ending in November of 2017, and data collection completed in (due to data lags for patient satisfaction, external hospital readmission, and mortality data) May of 2018.

### **ANALYSIS PLAN**

#### General Approach

The study analysis will have 3 phases. The primary analysis will examine our primary outcome, hospital readmission within 30 days, via an intention-to-treat analysis where comparisons will be made between the 2 study arms. We will then examine secondary outcomes of all cause ED visits to Vanderbilt or VHAN ED and mortality. Given VUMC's interest in understanding characteristics of patients not reached via telephone, we will explore differences among those called and reached, called and not reached, and the control arm. In these 3 phases we will examine outcome differences by treatment assignment, age, gender, race, highest educational attainment, health literacy, established primary care status, patient satisfaction level, Medicare readmission penalty diagnosis status, and readmission risk score calculated at discharge as part of routine care at VUMC. Lastly, we will use descriptive statistics to quantify the need for patient assistance with discharge plan implementation (appointment scheduling or reminders, questions about new medications, durable medical equipment acquisition, referral for new symptoms, etc.) among patients in the intervention arm who are called and reached.

#### Statistical Analysis

In our univariate analysis, differences among these patient characteristic groups will be assessed using the continuity corrected chi-square test or Mann-Whitney test for continuous outcomes and the Kruskal-Wallis test for categorical outcomes. In our multivariate analysis, we will examine the relationship between treatment assignment and our secondary endpoints using logistic regression. The study is not powered for a time-to-event analysis; however, we will explore time-to-readmission using the Cox proportional hazard model to understand the timing of when readmissions occur. In order to provide VUMC Leadership with preliminary efficacy data, we will perform an interim analysis at 50% enrollment ( $\sim$ 3.5 months) followed by the final analysis at study completion months ( $\sim$ 7 months). See **Appendix V** for details. We have pre-specified an  $\alpha$ -level of significance of 0.05 with penalties for a mid-study interim analysis per the O'Brian-Fleming alpha spending function allowing for an  $\alpha$ -significance level of 0.005 for the interim analysis and 0.048 for the final analysis.

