### Secondary Analyses:

- Subgroup Analysis of Primary Outcomes (forest plots + interaction analysis)
- Survival/Frequency Plot of Readmission events (0-45 days)
- Descriptive Demographics of Controls, Reached, Not Reached
- Heat Map of readmission rates by zip code

Figure 1 - Study Design Schematic and Enrollment Projection

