#### STUDY TIMELINE: UPDATED

- 1. Adult Executive Quality Committee 3 month Update June 21, 2017
- a. Analysis: [name] (descriptive, no outcome data)
  - Table 1 Patient demographics
  - Overall VUMC readmission rate
  - Summary of phone call nurse patient interventions
- b. Presenters: [name], [name], [name]
- 2. Blinded Interim Analysis 50% patient enrollment ~July 2017
- a. Content ([name])
  - 2 week analysis window: Alpha 0.005, no stopping/futility rules
  - Patient demographics (by study arm, Table 1)
  - VUMC readmission rate by study arm and assessment of significant difference
  - Pre-specified subgroup analysis for readmission yes/no
  - Will not include the reachability index at this time.
  - Will only use death data from VUMC and available Patient Satisfaction data
  - See Appendix V for details
- b. Safety Review August 2017
  - Safety Committee Members: [name], [name], [name]
  - Review of Discharge Phone Call RN's daily reports to her supervisors for safety issues.
  - Interim Analysis Preparation and Presentation: [name]
- 3. Enrollment End 100% patient enrollment end: ~Sept 20, 2017
- a. Readmit f/u end: ~Nov 5, 2017
- b. Freeze database after Patient Satisfaction data (2mo lag) included: ~Nov 20, 2017
- c. Re-open database to add death + external hospital readmission data (6-8mo lag): ~May 20, 2018
- d. Death date source: VUMC EHR
- e. External hospital readmission data source: Vanderbilt Health Affiliated Network (VHAN)
- 4. Adult Executive Quality Committee Presentation Study End Early Findings Jan 2018
- a. Final analysis findings, except for death data
- b. 2 week analysis window: Alpha 0.048
- 5. Final Analysis June 2018
  - a. Content ([name] and [name])
    - 2 week analysis window: Alpha 0.048
    - Patient demographics (by study arm, Table 1)
    - VUMC readmission rate by study arm and assessment of significant difference
    - Pre-specified subgroup analysis for readmission yes/no
    - Identical to the Interim Analysis plan except all patient satisfaction, external hospital readmission, and mortality data will be included.

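### The Statistical Analysis section assigns Kruskal-Wallis to categorical outcomes and ties the chi-square to continuous ones; reword it, and state whether the primary chi-square is continuity corrected

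*Combined protocol and SAP*

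**What the plan says.** The test sentence in Statistical Analysis covers univariate differences among patient characteristic groups and prescribes the "continuity corrected chi-square test or Mann-Whitney test for continuous outcomes and the Kruskal-Wallis test for categorical outcomes".

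Two other places set up the three-group comparisons to which it would apply. General Approach says "we will explore differences among those called and reached, called and not reached, and the control arm", and the list of secondary analyses includes "Descriptive Demographics of Controls, Reached, Not Reached". Appendix IV lists race and primary language, both nominal with several levels, among the baseline variables.

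For the primary outcome, General Approach specifies an intention-to-treat comparison of the two arms but names no test. The test has to be gathered from elsewhere:

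- The Study Summary gives "Power 90% (chi square" and "Sample size: 3556 (1778 per arm".
- The Table 1 footnote names a two-"group X^2 test of equal proportions (equal n's), 2-sided text, final analysis" alpha 0.048. The text after it says the authors "opted for a more conservative power target and detectable differences of 80% and 3.9% respectively".
- Appendix V puts the readmission rates in a 2x2 table, and the Study Timeline describes the final analysis as "Identical to the Interim Analysis plan except all patient satisfaction, external hospital readmission, and mortality data will be included".

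None of these mentions a continuity correction. The only chi-square named in Statistical Analysis is a corrected one.

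**The concern.** Kruskal-Wallis ranks its outcome. A nominal variable with three or more levels has no order to rank, so the result depends on which number each category happens to receive. The other half of the sentence, a chi-square for continuous outcomes, does not work either. The likely intention is a chi-square for categorical variables and rank tests for continuous ones.

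The plan stresses the institution's interest in who cannot be reached by telephone. If the sentence is programmed as written, part of that answer could change with a recoding that nobody would think to report.

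The second, smaller matter is the primary test. An unstated choice between a corrected and an uncorrected chi-square leaves the analyst some discretion over a result that is meant to inform an institution-wide investment decision.

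**Working it through.** **1. Dependence on coding**

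Inputs: group sizes 334 reached and 1117 called come from Sample Size Considerations, so 1117 − 334 = 783 not reached; 1117 controls come from Power Calculation. The documents contain no outcome or race data. The counts below are constructed, and five race levels are assumed because the Appendix IV list is broken in the available text.

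| | Black | White | Latino | Multiple | Unknown |
|---|---|---|---|---|---|
| Reached (334) | 50 | 261 | 13 | 3 | 7 |
| Not reached (783) | 164 | 541 | 39 | 8 | 31 |
| Control (1117) | 212 | 804 | 56 | 11 | 34 |

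- Kruskal-Wallis (tie-corrected, 2 df), levels coded in the order shown: H = 0.94, p = 0.62.
- Kruskal-Wallis, levels coded alphabetically: H = 9.04, p = 0.011.
- Of the 5! = 120 possible codings, 60 give p < 0.05.
- Pearson chi-square on the 3 x 5 table: 10.57 on 8 df, p = 0.23 under every order.

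The fault is confined to nominal variables with three or more levels. For a yes/no variable, Kruskal-Wallis equals (N − 1)/N times the Pearson chi-square, a factor of 2233/2234 here. For ordinal scores the ranking is meaningful.

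**2. Which chi-square do the plan's figures fit?**

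Formula per arm, two-sided, with p̄ the mean of the two rates and d their difference:

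n = [z(1−α/2)·√(2p̄(1−p̄)) + z(power)·√(p1(1−p1) + p2(1−p2))]² / d²

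With the continuity correction: n' = (n/4)·[1 + √(1 + 4/(n·d))]².

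Study Summary, 13.5% vs 10%, 90% power, α = 0.05:

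- n = [1.960 × 0.4554 + 1.2816 × 0.4547]² / 0.035² = 2.1766 / 0.001225 = 1776.8, so 1777, against the stated 1778.
- n' = 444.2 × [1 + √1.0643]² = 1833.5, so 1834.
- With 13.52% and α = 0.048 the results are again 1777 and 1834.
- Power at 1778 is 90.0% uncorrected and 89.1% corrected for either set of inputs. At 13.5% with α = 0.048 it is 89.7% and 88.7%.

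Table 1, control rate 13.52%, α = 0.048 (corrected version: d reduced by 1/n in the power formula):

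| n per arm, power | Printed rate / difference | Corrected: detectable rate | Uncorrected: detectable rate (difference) | Uncorrected difference rounded up, and implied rate |
|---|---|---|---|---|
| 1117, 80% | 9.6 / 3.9 | 9.62 | 9.70 (3.82) | 3.9, 9.62 |
| 1117, 90% | 9.1 / 4.4 | 9.07 | 9.15 (4.37) | 4.4, 9.12 |
| 1582, 80% | 10.2 / 3.3 | 10.22 | 10.28 (3.24) | 3.3, 10.22 |
| 1582, 90% | 9.7 / 3.8 | 9.74 | 9.80 (3.72) | 3.8, 9.72 |

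Rounding the corrected rates to the nearest 0.1 gives all four printed rates, and subtracting those from 13.52 gives the printed differences. Rounding the uncorrected differences up to the next 0.1, so that power is at least nominal, also gives all four printed differences, and subtraction gives the printed rates. Both routes reproduce all eight cells.

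**3. What the choice changes**

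- Power at α = 0.048, uncorrected vs corrected: 82.2% vs 80.4% (1117 per arm, 9.6%) and 89.7% vs 88.7% (1778 per arm, 13.5% vs 10%).
- Boundary example: 240 vs 201 readmissions of 1778 per arm gives chi-square 3.94, p = 0.047 uncorrected, and 3.74, p = 0.053 corrected. The critical value at 0.048 is 1.977² = 3.91.
- In simulation (400,000 trials per scenario) the two versions disagree in 1.0% of trials at 1778 per arm (13.5% vs 10%) and in 1.9% at 1117 (13.52% vs 9.6%).

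**The case against.** The best reply on the first matter is that this is a slip no competent analyst would follow, in exploratory comparisons, illustrated by counts chosen to make the point. Much of that stands. Under no true difference, a coding fixed in advance keeps its error rate (4.5% in 4000 simulated datasets, against 4.4% for the chi-square), and only 2.6% of those datasets had half or more of the codings significant. What remains is that the written rule is wrong for variables the plan intends to compare, and correcting it costs one sentence.

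Three stronger readings are tempting and are not supported:

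- A reader might infer that Mann-Whitney for continuous outcomes is also an error. It is valid for two groups, and the trial has two arms. The sentence merely lacks a correct three-group counterpart.
- A reader might infer that Table 1 was computed with the correction and therefore conflicts with 1778. Nearest rounding suggests this, but the documents state neither a correction nor a rounding rule, and a single uncorrected chi-square explains both Table 1 and the Study Summary if differences were rounded up.
- A reader might infer that the primary result is biased or materially underpowered. Either chi-square is a legitimate test of the two-arm comparison, and the power difference is 1 to 2 points.

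**Conclusion.** The test sentence is wrong as written, probably through a transposition, and should be corrected. The damage is limited to nominal characteristics with three or more levels in exploratory or descriptive comparisons. The 0.62 versus 0.011 contrast shows that coding can matter; it does not estimate how often it will, because the counts are constructed.

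The silence on the continuity correction is a minor specification gap. The uncorrected test matches 1778 (computed 1777, against 1834 corrected) and is compatible with Table 1 if differences were rounded up. The corrected test matches Table 1 by nearest rounding and gives about 89% power at 1778. The documents do not settle which was used. These figures rest on the pooled-variance normal approximation with equal arms.

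**What to change.** 1. Reword the sentence in Statistical Analysis: an r x c chi-square or Fisher exact test for categorical variables; Mann-Whitney for continuous or ordinal variables across two groups; Kruskal-Wallis for the same variables across three.
2. Add one sentence to General Approach or Statistical Analysis saying whether the primary two-sided chi-square at 0.048 is continuity corrected, fixed before outcome data are seen. Either version is acceptable. Table 1 need not be recomputed.
3. Optional, and not the repair of an error: prespecify a primary logistic model with arm and the readmission risk score, reported as a standardised risk difference with a simple rule for missing scores, and keep the unadjusted chi-square as supportive. Data Collection says the score is calculated before discharge, and randomisation follows discharge, so it is a proper baseline covariate. The gain depends on how well the score discriminates, which the documents do not give. Under an assumed AUC of 0.60 to 0.75 it would be roughly 0.4 to 3.9 power points.

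Items 1 and 2 cost two sentences and no new data. Item 3 uses a score already collected.
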